EFFICACY OF DELAYED COLOANAL ANASTOMOSIS FOR MEDIUM AND LOWER RECTUM CANCER TREATMENT. PHASE 2 CLINICAL TRIAL

CASCADOR Protocol

SYNOPSIS National multicentre trial

Version No. 7 of 11/08/2016 – IB No.: IB 2010-08

ClinicalTrials.gov Identifier: NCT01876901

RCB ID No. 2010-A00299-30

Coordinating Investigator

[name] [name]
Gastrointestinal Surgical Oncologist

Gastrointestinal Tumours Unit
Institut Bergonié

[name]

[contact] – [contact] Email: [contact]

Clinical and Epidemiological Research Unit

[name] [name]
Head of the Clinical and Epidemiological Research Unit

Institut Bergonié, Bordeaux, France

[name]
Biostatistician

Institut Bergonié, Bordeaux, France

[name]
Clinical Research Associate

Institut Bergonié, Bordeaux, France

[name], [name]
Bordeaux, France
Pharmacists

Institut Bergonié,

Economic analysis

[name] [name]
Doctor, Department of Medical Information

Institut Bergonié, Bordeaux, France

SPONSOR

INSTITUT BERGONIÉ

SYNOPSIS

Title of study	Efficacy of delayed coloanal anastomosis for medium and lower rectum cancer treatment. Phase II clinical trial. CASCADOR Protocol
Acronym	CASCADOR: ColoAnale Simple vs ColoAnale Différée en Oncologie Rectale (Simple Coloanal vs. Delayed Coloanal in Rectal Oncology)
Sponsor	Institut Bergonié Centre Régional de Lutte Contre le Cancer de Bordeaux et du Sud-Ouest (Regional Cancer Centre of Bordeaux and the South-West) [name]
Coordinator	[name] [name], Gastrointestinal Tumours Unit
Number of centres	
7 centres
 
ACAD (delayed coloanal anastomosis) group: 3 centres
 
 - FCCC (French Comprehensive Cancer Centre) Institut Bergonié, Bordeaux, France - Hôpital de la Croix-Rousse, CHU (University Hospital Centre) Lyon, - CHU Grenoble, 
ACAI (immediate coloanal anastomosis) group: 4 centres
 
 - FCCC Léon-Bérard, Lyon, France, - Hôpital d'Adultes de Brabois, CHU Vandoeuvre-lès-Nancy, - Centre Alexis Vautrin, Vandoeuvre-lès-Nancy, France - CHU Bordeaux
Indications	Medium and lower rectal cancer.
Study design	National multicentre phase II clinical trial
Number of patients	116 patients to be recruited (58 per group, see statistical analysis section).
Study duration	
Enrollment begins: 2nd quarter 2010
 
Enrollment ends: 30 April 2017
 
Patient follow-up period: 2 years
 
Study duration 9 years: 7 years of recruitment + 2 years of follow-up.

Primary objective	The aim of this study is to evaluate the efficacy of delayed coloanal anastomosis (ACAD) in the treatment of medium and lower rectal cancers at 30 days, in terms of symptomatic anastomotic fistula requiring a bypass stoma.
Secondary objectives	
 ▪ Evaluation of the efficacy of immediate coloanal anastomosis (ACAI) in the treatment of medium and lower rectal cancers at 30 days, in terms of symptomatic anastomotic fistula requiring a bypass stoma. ▪ According to the surgical technique used (ACAD or ACAI): 
 ○ Evaluation of the number of patients with a stoma (at 30 days, 1 year, and 2 years), ○ Evaluation of postoperative morbidity associated with coloanal anastomosis (at 30 days), ○ Evaluation of pre- and post-operative mortality (at 30 days), ○ Evaluation of progression-free survival (at 1 and 2 years), ○ Functional evaluation (quality of life, continence) (at 6 months, 1 year, and 2 years), ○ Evaluation of the duration of hospitalisation and economic impact (immediate or deferred costs, at 30 days, 1 year, and 2 years). ▪ Evaluation of the potential predictive role of the type of surgery on the occurrence of fistulas.
Inclusion criteria	
 1. Histologically proven rectal adenocarcinoma. 2. Medium or lower rectum tumour requiring removal of the entire rectum and its mesorectum. 3. T1 N+ or T2 N+ or T3 N+ or T3 N0 and M0 tumour. 4. Aged between 18 and 75 years inclusive. 5. ASA ≤ 2. 6. Sphincter continence compatible with coloanal anastomosis.

	
7. Patients who received preoperative radiotherapy alone or chemotherapy and radiotherapy.
 
8. Patient registered with a social security system.
 
9. For patients of childbearing age: use of contraception.
 
10. Patient information and signed and dated informed consent.

Exclusion criteria	
 1. Other histology of rectal cancer. 2. T1 N0 or T2 N0 or T4 tumour. 3. Metastatic disease M1. 4. History of cancer except cervical carcinoma in situ or basal cell carcinoma of the skin. 5. Patients who for psychological, social, family or geographical reasons could not be treated or followed up regularly according to the study criteria; patients deprived of liberty or under guardianship. 6. Pregnant or nursing women.
Evaluation criteria	
Primary evaluation criteria
 
The efficacy of each surgical procedure (ACAD and ACAI) will be evaluated in terms of patients with no symptomatic anastomotic fistula requiring a bypass stoma (ileostomy or colostomy, whether preventive or curative) for treatment in the first 30 days after surgery.
 
An anastomotic fistula is defined by:
 
 the escape of faeces through a drainage system, if one is present, or a set of clinical signs (fever, subocclusion, etc.) requiring confirmation by pelvic scan (collection of fluid plus gas in the perianastomatal area). 
Secondary evaluation criteria
 
 ■ The number of bypass stomas (preventive or therapeutic) will be evaluated. ■ Morbidity will be assessed in terms of grade 3 and 4 surgical complications according to the Dindo classification of surgical complications and the NCI-CTCAE V3 toxicity scale. ■ Post-operative mortality will be assessed during the first 30 days after the date of surgery. ■ Progression-free survival will be assessed at 1 and 2 years. This is defined as the time between the date of the surgery and the date of the earliest of the following events: 
 ○ The patient's death, whatever the cause, ○ Local or distant progression. ■ A functional assessment will be conducted in the month prior to surgery and at 6 months, 1 year, and 2 years after surgery: 
 ○ Quality of life will be assessed using self-administered EORTC QLQ-C30 questionnaire and its colorectal module QLQ-CR38. ○ Digestive functions, in particular anal incontinence, will be evaluated using the 5-item Jorge and Wexner scale. ○ An economic impact study will be conducted. Economic impact (hospitalisation, re-hospitalisation) will be evaluated using data from the French hospital discharge database (PMSI). The use of consumables during the operation and the fitting of temporary or permanent colostomy bags or ileostomy bags (loss of sphincter on fistula) until the eventual restoration of intestinal continuity will be evaluated.
Description of treatments	
Whatever the mode of continuity restoration used, resection is the same in the two groups. It consists of total excision of the rectum and its mesorectum, whether the procedure is performed by laparotomy or laparoscopy.
 
 • ACAD group (Delayed Coloanal Anastomosis) 
After surgical resection, the colon is exteriorised through the anus and attached to the buttock with two stitches.
 
On or around day 6, the exteriorised colon is resected and the coloanal anastomosis is performed without a preventive bypass stoma.
 
 • ACAI group (Immediate ColoAnal Anastomosis) 
After surgical resection, coloanal anastomosis is usually performed after creation of a J-pouch, when possible. In most cases, a preventive stoma is created.

	If there is no fistula, the patient will undergo another surgery for closure of the bypass stoma.																																																							
Monitoring methods and duration	
A 30-day complications assessment will be done at the postoperative consultation (i.e. approximately 40-45 days after surgery, in practice).
 
6 months after surgery, functional results will be assessed using quality of life questionnaires.
 
Patients will be seen again at the 1- and 2-year postoperative marks to assess the functional outcome of their digestive system, using quality of life questionnaires. Their final recovery status will also be recorded.
 
Patients will be monitored according to the usual follow-up of each surgeon.
																																																							
Study timeline	
  
 	Inclusion	S U R G E R Y	40-45 days post-op	6 months after surgery	1 year after surgery	2 years after surgery	
   
 Inclusion/exclusion criteria	X						
 
 Informed consent signed	X						
 
 Pre-anaesthetic assessment	X						
 
 Quality of life questionnaires	X		X	X	X	X	
 
 Assessment of complications		X					
 
 Functional digestive outcomes (stoma)		X	X	X	X	X	
  
								Inclusion	S U R G E R Y	40-45 days post-op	6 months after surgery	1 year after surgery	2 years after surgery	Inclusion/exclusion criteria	X						Informed consent signed	X						Pre-anaesthetic assessment	X						Quality of life questionnaires	X		X	X	X	X	Assessment of complications		X					Functional digestive outcomes (stoma)		X	X	X	X	X
	Inclusion	S U R G E R Y	40-45 days post-op	6 months after surgery	1 year after surgery	2 years after surgery																																																		
Inclusion/exclusion criteria	X																																																							
Informed consent signed	X																																																							
Pre-anaesthetic assessment	X																																																							
Quality of life questionnaires	X			X	X	X	X																																																	
Assessment of complications			X																																																					
Functional digestive outcomes (stoma)			X	X	X	X	X																																																	
Statistical analysis	
Determining the number of patients
 
 ACAD group 
The primary judgement criterion was the efficacy of ACAD surgery as measured by the absence of fistula requiring a bypass stoma. We wish to demonstrate that the rate of patients with a fistula requiring a bypass stoma is less than 15%, i.e. the efficacy rate of ACAD is greater than 85%. Based on a one-sided binomial test with null and alternative hypotheses of 85% and 95% respectively, 53 eligible and evaluable ACAD patients will be required (one-sided type I error of 5% and power of 80%). If 49 or more patients (out of 53) have no fistula requiring a bypass stoma, then we will conclude that ACAD is effective. In order to anticipate possible non-evaluable patients, we plan to recruit 58 ACAD patients.
 
 ACAI group 
In parallel, we plan to recruit 58 ACAI patients.
 
Statistical analysis
 
 Quantitative variables: number of values, number of missing data, mean, standard deviation, 95% confidence interval, median, 1st and 3rd quartiles, minimum and maximum. Qualitative variables: number of values, number of missing data, frequency, percentage for each variable modality and exact confidence interval of each modality. Survival data: Kaplan-Meier method, median survival times with 95% confidence interval, median follow-up (follow-up) using the reverse Kaplan-Meier method, 																																																							
Benefits	Putting forward a surgical technique associated with low morbidity for patients treated for medium and lower rectal cancer.

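### PFS is reported by technique in groups fixed by centre, with only crude Kaplan-Meier summaries visible, so a difference in nodal stage or preoperative treatment could be misread as a technique effect

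*Combined protocol and SAP*

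**What the plan says.** Under Secondary objectives, the Synopsis lists the outcomes to be evaluated according to technique (ACAD or ACAI). One of them is "Evaluation of progression-free survival (at 1 and 2 years". Evaluation criteria defines the endpoint as time from surgery to death from any cause or to local or distant progression, whichever comes first.

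Number of centres assigns technique by site: "ACAD (delayed coloanal anastomosis) group: 3 centres" and "ACAI (immediate coloanal anastomosis) group: 4 centres". No centre appears in both lists. Study design reads "National multicentre phase II clinical trial". Randomisation, matching and stratification are not mentioned.

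Inclusion criteria admit patients with different prognoses: "T1 N+ or T2 N+ or T3 N+ or T3 N0 and M0 tumour", and "Patients who received preoperative radiotherapy alone or chemotherapy and radiotherapy".

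For analysis, the Statistical analysis section offers "Survival data: Kaplan-Meier method, median survival times with 95% confidence interval", followed by median follow-up by reverse Kaplan-Meier. The item then ends on a comma. No covariate, stratification factor or caution about interpretation is visible.

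**The concern.** When technique is decided by where a patient is treated, the two PFS curves differ by whatever separates the patients of the two sets of centres, as well as by technique. Nodal status is an obvious candidate. The eligible population divides into T3 N0 patients and T1-T3 N+ patients, and nothing in the design makes the two groups share the same proportions. The preoperative regimen may also vary by centre.

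Both factors have to be known at inclusion, before surgery, because eligibility depends on them. They can therefore be used without new data, and neither can be a consequence of the technique.

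What is at stake is the oncological message. A delayed anastomosis group with more N+ patients could look oncologically worse, and one with fewer could look better, when technique has no effect on progression.

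**Working it through.** **Plan figures.** None is stated for PFS: no expected rate, hazard ratio, event count or stage mix. The only sized hypothesis is the single-arm test of ACAD on fistula, which does not enter here. The inputs from the documents are the group sizes, 58 + 58 = 116 (Number of patients), and the 2-year follow-up (Study duration).

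**Assumptions (not in the documents).**
- Technique has no effect on PFS.
- 2-year PFS is 85-90% in N0 and 70-75% in N+.
- The N+ share is 40% in one group and 60-70% in the other.
- There is no censoring before 2 years.

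**Step 1: crude difference.** Group PFS = S(N0) × (1 − p) + S(N+) × p, where p is the N+ share. The spurious difference is therefore [S(N0) − S(N+)] × (difference in p).

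- Smallest case, 85% and 75%, shares 40% and 60%: 0.85 × 0.60 + 0.75 × 0.40 = 0.81, against 0.85 × 0.40 + 0.75 × 0.60 = 0.79. Difference: 2 points.
- Largest case, 90% and 70%, shares 40% and 70%: 0.90 × 0.60 + 0.70 × 0.40 = 0.82, against 0.90 × 0.30 + 0.70 × 0.70 = 0.76. Difference: 6 points.

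**Step 2: random error of the same quantity.** The 95% half-width of a between-group difference is 1.96 × √{[S₁(1 − S₁) + S₂(1 − S₂)] / 58}.

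- 0.81 and 0.79: 1.96 × √(0.3198 / 58) = 14.6 points; 2 / 14.6 = 14%.
- 0.82 and 0.76: 1.96 × √(0.3300 / 58) = 14.8 points; 6 / 14.8 = 41%.

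The artefact is smaller than the random error. It is systematic, however, so the confidence interval does not show it. If a reader formed that nominal 95% interval, it would exclude no difference in about 6% of trials in the smallest case (shift 0.020 / 0.0743 = 0.27 standard errors). In the largest case it would do so in about 12.5% (0.060 / 0.0754 = 0.80 standard errors). The nominal figure is 5%.

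**Step 3: effect of standardising.** In the largest case the pooled N+ share is (0.40 + 0.70) / 2 = 0.55. Both groups then give 0.90 × 0.45 + 0.70 × 0.55 = 0.79, and the difference is 0. This is exact only because nodal status is the sole difference built into the example.

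**Step 4: information available.** Expected events are 116 × (1 − S): 11.6 at 2-year PFS of 90% and 34.8 at 70%, so about 12 to 35. That leaves room for very few adjustment factors.

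**Sensitivity to the assumptions.** With strata from 90/80% to 90/65% and high-risk shares from 50 versus 60% to 30 versus 70%, the difference runs from 0.10 × 0.10 = 1 point to 0.25 × 0.40 = 10 points. The contribution of preoperative treatment was not quantified.

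**The case against.** The strongest reply is that the plan makes no PFS comparison. It shows no log-rank test, hazard ratio or margin for PFS. ACAI is recruited in parallel without a hypothesis of its own, and the one objective about an effect of the type of surgery concerns fistulas. This stands. A reader might infer that the trial sets out to estimate a technique effect on PFS, but the documents do not support that. The risk that remains is misreading. It is a real one, because the expanded acronym sets simple against delayed anastomosis, PFS is reported by technique, and no visible sentence calls the result descriptive.

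A reader might also infer that stage and preoperative treatment are left out of the full analysis. That cannot be established. The document is a synopsis and its survival item ends on a comma, so text may be missing. The absence of adjustment holds only for what is visible.

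Eligibility also narrows case mix: T1 N0, T2 N0, T4 and M1 tumours are excluded, ASA is at most 2, age is capped at 75, and all patients have had radiotherapy. This limits the imbalance, but N0 and N+ patients and two regimens remain.

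Finally, adjustment cannot separate technique from centre or surgeon, because technique is wholly nested in centre. If the regimen follows centre policy, overlap may be too poor to adjust for it. Both points stand and shape the fix.

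**Conclusion.** The point holds as a caution about interpretation, with an inexpensive remedy. Crude PFS by technique can carry a case-mix difference that the visible plan neither adjusts for nor flags. Under the stated assumptions the artefact is 2 to 6 points of 2-year PFS, or 14% to 41% of the half-width of the between-group difference.

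It would be tempting to say that the bias rivals the statistical error. It does not: that impression comes from setting a between-group difference against the narrower interval of a single group. The direction is unknown, every rate and share is assumed, and PFS is an unpowered secondary endpoint. The primary conclusion on fistula is unaffected. Label: cheap improvement.

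**What to change.** Keep the crude Kaplan-Meier curves and add the following to the Statistical analysis section:

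- A table of nodal status and preoperative treatment by group, as established at inclusion.
- As a sensitivity analysis, 1- and 2-year PFS by technique, standardised to the pooled distribution of nodal status (N0 or N+). Include preoperative treatment (radiotherapy alone or with chemotherapy) only if both regimens occur in both groups.
- A statement that PFS by technique is descriptive, and that centre and surgeon differences remain unadjusted.

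Naming the factors in advance prevents their being chosen after the curves are seen. Two is a sensible limit, given the few events expected.

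The cost is a few lines of text and one extra table, with no new data. The standardised estimate will be less precise than the crude one; how much less depends on the overlap between groups, which the documents do not show. Differences in T stage among N+ patients would also remain.

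### The 49-of-53 rule has an exact one-sided type I error of 8.5%, not the stated 5%, and the synopsis does not fix which ACAD patients form the 53

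*Combined protocol and SAP*

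**What the plan says.** The sample-size text (Synopsis, Statistical analysis, ACAD group) sets a one-sided binomial test of 85% against 95%, with 5% type I error and 80% power. It arrives at "53 eligible and evaluable ACAD patients". The decision rule is: "If 49 or more patients (out of 53) have no fistula requiring a bypass stoma, then we will conclude that ACAD is effective". The target is raised to 58 for this reason: "In order to anticipate possible non-evaluable patients, we plan to recruit" that number.

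Under the primary criterion (Synopsis, Evaluation criteria), the efficacy of each procedure "will be evaluated in terms of patients with no symptomatic anastomotic fistula requiring a bypass stoma", where the stoma is one made "for treatment in the first 30 days after surgery". The ACAD procedure (Synopsis, Description of treatments) has two stages: "On or around day 6, the exteriorised colon is resected and the coloanal anastomosis is performed without a preventive bypass stoma". Deaths within 30 days, grade 3 and 4 complications and the number of stomas are secondary criteria.

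The synopsis does not define evaluable or name an analysis set. It gives no cut-off for a denominator other than 53. It does not say how to score a patient who dies without a fistula or whose anastomosis is never made.

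**The concern.** There are two faults, and both concern the single decision the trial is built to make.

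First, the cut-off does not deliver the error rate claimed for it. If the true fistula-free rate is 85%, the written rule calls ACAD effective more often than one time in twenty.

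Second, the denominator is open. ACAD has an interval of about six days in which a patient has been resected but has no anastomosis. A patient who dies or stops in that interval has no anastomosis that could leak. Such a patient could be kept as fistula-free or set aside as non-evaluable. With 58 recruited and 53 needed, there is room for five to be set aside. One patient separates pass from fail, so a reader should be able to see that this choice was made before the results were known.

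**Working it through.** **Inputs.** From the Statistical analysis section: p0 = 0.85, p1 = 0.95, one-sided alpha 0.05, power 0.80, n = 53, cut-off 49, recruitment 58. No rate of death or uncompleted anastomosis is given, so steps 4 and 5 use assumed rates of 1, 2 and 3 percentage points.

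**Step 1: reproduce the plan's figures.** The arcsine approximation gives n = [(1.6449 + 0.8416) / (2·asin√0.95 − 2·asin√0.85)]² = (2.4865 / 0.34437)² = 52.1, rounded up to 53. The matching critical count is 53·sin²(asin√0.85 + 1.6449/(2√53)) = 48.8, hence 49. Both figures in the plan reproduce, but from an approximation.

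**Step 2: exact error of the written rule.** With f failures allowed, the chance of passing is the sum over f of C(53,f)·(1−p)^f·p^(53−f).

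- At p = 0.85, f = 0 to 4: 0.0002 + 0.0017 + 0.0078 + 0.0234 + 0.0516 = 0.0846 (unrounded terms).
- At p = 0.95, f = 0 to 4: 0.0660 + 0.1840 + 0.2518 + 0.2253 + 0.1482 = 0.875.
- Stopping at f = 3 (50/53): 0.0331 and 0.727.

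**Step 3: exact cut-offs for other denominators.** These are the smallest counts with alpha at or below 5%.

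| Analysed | Cut-off | Alpha | Power at 95% |
|---|---|---|---|
| 53 | 50 | 3.3% | 72.7% |
| 54 | 51 | 3.0% | 71.6% |
| 55 | 52 | 2.6% | 70.5% |
| 56 | 53 | 2.4% | 69.3% |
| 57 | 54 | 2.1% | 68.2% |
| 58 | 55 | 1.9% | 67.0% |
| 59 | 55 | 4.7% | 82.8% |

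Four failures in 58 (54/58) gives 5.19%, just over the limit. From 53 to 58 patients at most 3 failures are allowed, so power falls as n rises. The first n that meets both design targets is 59, one more than the recruitment target.

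**Step 4: effect of the open denominator on a stricter count.** Suppose death and uncompleted anastomosis counted as failures, and the true success rate on that count were 85%. (The plan set 85% for fistula alone.) The chance of passing is then:

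| Assumed event rate | 49/53, scored fistula-free | 49/53, excluded and replaced | 50/53, scored fistula-free | 50/53, excluded and replaced |
|---|---|---|---|---|
| 0 | 8.5% | 8.5% | 3.3% | 3.3% |
| 1 point | 11.9% | 11.4% | 5.0% | 4.7% |
| 2 points | 16.4% | 15.1% | 7.3% | 6.6% |
| 3 points | 22.2% | 19.9% | 10.6% | 9.3% |

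The scored columns use p = 0.85 + e, and the excluded columns p = 0.85/(1 − e).

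**Step 5: how often the two counts would disagree.** With a 95% fistula-free rate, the fistula-only result passes and the stricter one fails with probability P(X ≥ k | 0.95) − P(X ≥ k | 0.95 − e). At 50/53 this is 12.1%, 24.0% and 34.9% for e of 1, 2 and 3 points.

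**Step 6: direction on the plan's own endpoint.** A patient who dies without a fistula is literally a success. Excluding that patient changes 49/53 = 92.5% to 48/52 = 92.3%, slightly against ACAD.

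**The case against.** The strongest reply concerns the second fault. The document is a synopsis, and analysis sets are normally defined in the full text. A fistula-specific primary criterion is legitimate, and under its own 85% null, scoring a fistula-free death as a success inflates nothing. Deaths, severe complications and stomas are all reported as secondary criteria, so nothing is hidden. Technique is tied to centre (three ACAD, four ACAI), which goes some way to fixing the planned technique in advance.

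Most of this stands. A reader might infer that leaving these events unscored can only favour ACAD. The documents do not support that. It is true only against a composite in which the events are failures, and the plan neither adopts nor needs one. Step 6 shows that exclusion can run the other way. So can a leak before the anastomosis that is treated with a stoma, which might meet the definition "the escape of faeces through a drainage system, if one is present" and count as a failure. Nor does the disagreement in step 5 show bias: it compares two different endpoints.

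What survives is narrower. Separate secondary counts need not show how the events overlap, nor identify an uncompleted anastomosis without a stoma. Listing centres by technique does not say what happens to a patient whose technique changes, and the resection itself does not distinguish the groups: "Whatever the mode of continuity restoration used, resection is the same in the two groups".

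None of this touches the cut-off. One might say that 8.5% is tolerable in phase II, but the plan states 5%.

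**Conclusion.** The cut-off is wrong as written. A 49/53 rule has an exact one-sided type I error of 8.5% against a stated 5%. This follows from the plan's own inputs and needs no outside assumption. Correcting it at the planned size brings power below the stated 80%, to between 67.0% and 72.7% depending on how many of the 58 are analysed.

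The undefined decision set is a gap in the available text that should be closed. It does not show that the trial had no rule, and it is not a bias in the fistula-only endpoint. Its size cannot be estimated from the documents: step 4 depends entirely on assumed event rates and on applying the 85% threshold to a count it was not set for. The point rests on the ordering of events (window from resection, anastomosis around day 6) and on a one-patient margin.

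**What to change.** 1. Replace the fixed 49/53 rule with the exact cut-off for the number actually analysed (at most 3 failures for 53 to 58 patients) and restate the power. If 80% power is to be kept, 59 analysed patients with at most 4 failures achieve it.
2. Define the ACAD decision set as all eligible patients resected with ACAD recorded beforehand as the planned technique. Do not exclude for death, uncompleted anastomosis or change of technique. List any other exclusions with reasons.
3. Keep the fistula-only primary criterion and state that such patients without a fistula score as fistula-free. State also whether a leak before the anastomosis that is treated with a stoma meets the fistula definition.
4. Report beside the primary result one prespecified analysis of the same set that counts death within 30 days and anastomosis not completed by day 30 as failures, with an exact confidence interval. If the two disagree, say that effectiveness refers to fistula only.

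The cost is wording and one extra result line. Mortality and complications are already collected; planned technique and completion of the anastomosis are assumed to be in the operative record. The downsides are a lower stated power, which comes from the cut-off and not from these events, and a second result that may be somewhat less favourable.

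### The success rule of 49 out of 53 has an exact one-sided type I error of 8.5%, not the stated 5%, and no cut-off at 53 patients gives both 5% and 80% power

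*Combined protocol and SAP*

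**What the plan says.** All the relevant text is in the synopsis, under Statistical analysis, Determining the number of patients, ACAD group. Efficacy is the absence of a fistula requiring a bypass stoma, and the aim is to show a rate above 85%.

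- The test: "Based on a one-sided binomial test with null and alternative hypotheses of 85% and 95% respectively".
- The error rates: "one-sided type I error of 5% and power of 80" (per cent).
- The sample size: "53 eligible and evaluable ACAD patients".
- The decision rule: "If 49 or more patients (out of 53) have no fistula requiring a bypass stoma, then we will conclude that ACAD is effective".
- The allowance for losses: "In order to anticipate possible non-evaluable patients, we plan to recruit" 58 ACAD patients. No cut-off is given for any evaluable number other than 53.

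The section mentions no approximation and no other significance level. The immediate-anastomosis (ACAI) group has a recruitment target but no hypothesis or success rule.

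**The concern.** A cut-off, a sample size and two hypothesised rates together fix the type I error and power of a single-group binomial rule. Those two figures can therefore be checked directly against the ones stated. When the check is made, the rule does not have the 5% type I error claimed for it.

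This is the only decision rule in the plan, and it is what would support a claim that the efficacy of ACAD exceeds 85%. If exactly 49 of 53 patients succeed, the rule calls ACAD effective although the named test does not reject 85% at the 5% level. The plan also asks for exact confidence intervals on qualitative variables. At 49 of 53 the exact 90% interval, which corresponds to a one-sided 5% test, still contains 85%. The report could then contain a positive conclusion beside an interval that does not support it.

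**Working it through.** **Inputs**, all from the synopsis section cited: null rate p0 = 0.85; alternative p1 = 0.95; one-sided type I error 0.05; power 0.80; n = 53; success if X ≥ 49, where X is the number of patients without the event.

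**Step 1. Where 53 and 49 probably come from.** The arcsine approximation gives

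n = [(z₀.₉₅ + z₀.₈₀) / (2·arcsin√0.95 − 2·arcsin√0.85)]² = [(1.645 + 0.842) / (2.6906 − 2.3462)]² ≈ 52.1, rounded up to 53.

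Its critical count at n = 53 is 53·sin²(arcsin√0.85 + 1.645/(2√53)) = 48.8, so 49. Its nominal p-value at 49/53 is 0.041 and its nominal power is 0.806. Both numbers in the plan therefore follow from one approximation. This is an inference; the document does not name the method.

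**Step 2. Exact error rates of the rule as written.** With P(X ≥ r | p) = Σₖ₌ᵣ⁵³ C(53,k)·pᵏ·(1−p)⁵³⁻ᵏ:

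| Cut-off at n = 53 | Type I error (p = 0.85) | Power (p = 0.95) |
|---|---|---|
| ≥ 48 | 0.1739 | 0.9518 |
| **≥ 49 (plan)** | **0.0846** | **0.8754** |
| ≥ 50 | 0.0331 | 0.7271 |
| ≥ 51 | 0.0097 | 0.5018 |

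For the plan's cut-off at p = 0.85, the terms for 49, 50, 51, 52 and 53 successes are 0.0516 + 0.0234 + 0.0078 + 0.0017 + 0.0002, which is 0.0846 before rounding of the terms. The ratio to the stated figure is 0.0846/0.05 = 1.7.

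The type I error falls and power falls as the cut-off rises. The lowest cut-off with error at or below 5% is 50, and its power is already below 80%. So no cut-off at n = 53 meets both figures. For reference, the smallest exact design that does is 55 of 59 (type I error 0.0469, power 0.8281).

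**Step 3. Do other versions of the test rescue 49/53?** The normal approximation without continuity correction has a critical count of 53·0.85 + 1.645·√(53·0.85·0.15) = 45.05 + 1.645·2.600 = 49.3, so 50 are needed. The p-values at 49/53 are:

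- exact: 0.085
- normal: 0.064
- normal with continuity correction: 0.092
- mid-p: 0.059
- arcsine: 0.041

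Only the arcsine version falls below 0.05.

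**Step 4. Agreement with the exact interval.** The one-sided 95% Clopper-Pearson lower bound (the lower limit of the 90% interval) is 83.6% for 49/53 and 86.0% for 50/53. The first does not exclude 85%; the second does.

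**Step 5. Evaluable numbers other than 53.** With all 58 evaluable, 54/58 has a type I error of 0.0519 and power 0.836, just missing 5%. The exact cut-off is then 55/58, with type I error 0.0187 and power 0.670.

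**The case against.** The strongest reply is that the plan is not careless. Its sample size and cut-off agree with each other under the arcsine approximation, the text does not describe the test as exact, and planning with an approximation is common. That stands as an explanation of where the numbers came from. It does not support the stated 5%: the count of fistula-free patients is binomial whatever formula set the cut-off, and the written rule accepts a true 85% rate 8.46% of the time.

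A second reply is that this is a phase II trial, where an error rate of 8.5% or more may be acceptable. It may be, but the plan says 5%, so the remedy on that view is to state the real figure.

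A third is that only one result is affected. Moving from 49 to 50 changes the conclusion only when exactly 49 of 53 succeed. That is true, but such a result is not rare. Its probability is 0.0846 − 0.0331 ≈ 0.05 if the true rate is 85%, and 0.8754 − 0.7271 ≈ 0.15 if it is 95%.

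Finally, the written rule has more power than stated (87.5% against 80%), so only the type I error is wrong in the unfavourable direction. The missing cut-offs for other evaluable numbers are a gap beside the arithmetic error, not part of it.

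**Conclusion.** The concern holds. The stated cut-off and the stated type I error are incompatible under the binomial test that the plan names: 8.46% against 5%. At 53 patients the plan can have a type I error within 5% (50/53: 3.3%, power 72.7%) or power of at least 80% (49/53: 87.5%, type I error 8.5%), but not both.

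The result rests only on the plan's own inputs and on independent patients sharing one success probability. The arcsine origin of 53 and 49 is inferred, and the conclusion does not depend on it. Only the synopsis was available for this check.

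**What to change.** Choose one of two options and record the choice before the primary result is known.

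1. **Keep the type I error within 5%.** Replace the rule with: *ACAD will be judged effective if at least 50 of 53 evaluable patients are free of a fistula requiring a bypass stoma (exact one-sided type I error 3.3%, power 73% at a true rate of 95%).*
2. **Keep 49 of 53.** Restate the one-sided type I error as 8.5% and the power as 87.5%.

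The first is the closer match to the plan's stated 5%. Under either option, name the test as exact binomial and give the cut-off for the number actually evaluable. For option 1 these are the smallest counts with an exact type I error at or below 5%:

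| Evaluable | 50 | 51 | 52 | 53 | 54 | 55 | 56 | 57 | 58 |
|---|---|---|---|---|---|---|---|---|---|
| Successes needed | 47 | 48 | 49 | 50 | 51 | 52 | 53 | 54 | 55 |

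Neither option needs more patients. Option 2 changes wording only. Option 1 changes the primary success criterion, and its price is a stated power of 73% in place of 80% (67% if all 58 are evaluable). The price of option 2 is a more lenient error rate stated openly.
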